4.5.7.2 Description of Clinical Outcome Assessment Instruments SLEDAI-2K

The SLEDAI-2K is a validated instrument to assess SLE disease activity (see Appendix 9). It evaluates clinical symptoms and laboratory markers across nine organ systems and will be used to capture changes in lupus-related disease activity. SLE manifestations are assessed by the clinician if present within the last 30 days and added to determine the total SLEDAI-2K score, which ranges from 0 to 105. The SLEDAI-2K

score is to be taken at baseline, several subsequent scheduled visits throughout the study (see schedule of activities in Appendix 1), at an early study discontinuation visit, and at any unplanned visit related to a suspected extrarenal or lupus nephritis flare. It must be completed if new or worsening lupus symptoms or flares are observed at a scheduled visit when SLEDAI-2K is not part of the standard assessments.

FACIT-F Scale

The FACIT—F Scale is a patient-completed questionnaire consisting of 13 items that assess fatigue and has been validated in patients with SLE (Kosinski et al. 2013). Instrument scoring yields a range from 0 to 52, with higher scores representing better patient status (less fatigue). This questionnaire should be completed by the patient prior to any procedures being performed at the visit, if possible. The form should then be checked by site staff for completeness. A copy of the questionnaire can be found in Appendix 10.

SF-36 v2 (Acute Version)

The SF-36 v2 (Acute Version) is a 36-item generic health status measure that has been validated in patients with SLE (Stoll et al. 1997). It measures eight general health domains: physical functioning, role physical, bodily pain, general health, vitality, social functioning, role emotional, and mental health. These domains can also be summarized as physical and mental component scores. This questionnaire should be completed by the patient prior to any procedures being performed at the visit, if possible. The form should be checked for completeness by the site staff. A copy of the questionnaire can be found in Appendix 11.

EQ-5D-5L

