Appendix 10 FACIT-Fatigue

(Sample; Not to Be Used to Enter Subject Data)

FACIT Fatigue Scale (Version 4)

Below is a list of statements that other people with your illness have said are important. Please circle or mark one number per line to indicate your response as it applies to the past 7 days.

		Not at all	A little bit	Some- what	Quite a bit	Very much
HI7	I feel fatigued	0	1	2	3	4
H1112	I feel weak all over	0	1	2	3	4
Anl	I feel listless ("washed out")	0	1	2	3	4
An2	I feel tired	0	1	2	3	4
An3	I have trouble starting things because I am tired	0	1	2	3	4
An4	I have trouble finishing things because I am tired	0	1	2	3	4
An5	I have energy	0	1	2	3	4
An7	I am able to do my usual activities	0	1	2	3	4
An8	I need to sleep during the day	0	1	2	3	4
An12	I am too tired to eat	0	1	2	3	4
Anl4	I need help doing my usual activities	0	1	2	3	4
An15	I am frustrated by being too tired to do the things I want					
	to do	0	1	2	3	4
Anl6	I have to limit my social activity because I am tired	0	1	2	3	4

 English (Universal)
 16 Nevember 2007

 Copyright 1987, 1997
 Page I of

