Missing data will be imputed by multiple imputations using FCS predicted mean matching method. A set of candidate donors with 5 members is chosen for the predictive mean matching method. Only patients who did not experience death will be included in the imputation model. Separate imputation models will be used for each treatment group.

The models will contain the following variables (in order of being imputed):

- Baseline eGFR
- Log-serum Albumin at Baseline
- Region (stratification factor)
- Race (stratification factor)
- Sex
- Age
- BMI
- Week 24 eGFR
- Week 36 eGFR
- Week 50 eGFR
- Week 64 eGFR
- Log-serum Albumin at Week 76
- Week 76 eGFR

The imputation will be implemented using the following three standard steps to generate inference from the imputed data. The number of imputations will be set of 100.

1. Imputation step:

- The missing data will be imputed 100 times to generate 100 imputed datasets for the patients who did not experience death.
- Patients who experienced death will be added in each of the datasets to obtain full datasets including all the patients in the analysis population.
- A number of burn-in iterations of 100 and a seed of 5678234 will be used.
- Analysis step: Each of the 100 imputed datasets will be analyzed using ANCOVA model
- 3. **Pooling step:** The results from the 100 imputed datasets will be combined for inference following the methodology developed by Rubin (Rubin 1987).

4.3.1.6 Change in FACIT-F scale from Baseline to Week 76

Change in FACIT-F scale from baseline at Week 76 will be analyzed using ANCOVA model. The response variable in the model will be change in FACIT-F scale from baseline at Week 76. Treatment group, baseline FACIT-F scale and the stratification factors race and region will be included in the model as independent variables. The adjusted difference between the treatment group with 95% CI and p-value will be presented.

The FACIT-F scale for patients who died will be imputed with 0 (composite strategy). All other intercurrent events (specified in Section 4.3) will be handled using treatment policy strategy.

Missing data will be imputed by multiple imputations. Only patients who did not experience death will be included in the imputation model. Multiple imputation methods will be the same as described in Section 4.3.1.5.

The multiple imputation models will contain the following variables (in order of being imputed):

- Baseline FACIT-F score
- Region (stratification factor)

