analysis will only include patients who would reach to the specified visit at the time
of CCOD (patients who moved to OLT or SFU period or withdraw from the study
prior to endpoint assessment, but would otherwise reach to the assessment visit by
CCOD will be included).

Last Observation Carry Forward (LOCF) will be used as the missing data imputation method. Twenty-four-hour UPCR will be imputed in the following order:

- 1. Spot UPCR at the same visit
- 2. 24-hour UPCR at the previous visit
- 3. Spot UPCR at the previous visit

The endpoint proportion of patients who achieve CRR with successful prednisone taper at post-Week 76 weeks will be evaluated as achievement of CRR at the endpoint assessment visit with the following:

 No receipt of prednisone >7.5 mg/day (or equivalent) from 12 week prior to the endpoint assessment visit The endpoint proportion of patients who experience death or renal-related events through the post-Week 76 visits will be evaluated from the beginning of the study.

The change from baseline for eGFR and FACIT-F post Week 76 will be summarized using descriptive statistics. A 95% CI of mean difference between the treatment groups will be presented.

Estimand attributes for the change from baseline for eGFR and FACIT-F are defined as follows:

- Population: Patients with active or active/chronic ISN/RPS 2003 Class III or IV proliferative LN who meet the adequate response criteria at Week 76.
- Endpoint (variable): Change from baseline for eGFR and FACIT-F at Week 106, 132, 158, 184, and 210.
- Treatments:
 - Experimental: Obinutuzumab 1000 mg IV infusion start at Day 1 and Week 2,
 24, 26, and either Weeks 50 and 52 or Week 52 only, Week 80 for every
 6 months until the study unblinded to investigator and patients
 - Control: Placebo
- Intercurrent events: rescue therapy, treatment failure, study treatment discontinuation, death, entering into OLT or entering into SFU prior to endpoint assessment. The treatment policy strategy will be used for all the intercurrent events with the exception of death. Data after death will be imputed with 0.

It is noted that the "Clinically significant, sustained worsening in UPCR and/or eGFR from Week 24 onward that leads the investigator to conclude the patient has failed the randomized treatment regimen" criteria of the treatment failure was not evaluated post Week 76.

Summary measure: Difference in means at a specified visit of interest.

LOCF will be used as missing data imputation method.

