Daily / Role Functioning	An7	I am able to do my usual activities	3 = Quite a bit 4 = Very Much
	An8	I need to sleep during the day	
	An12	I am too tired to eat	
	An14	I need help doing my usual activities	
	An15	I am frustrated by being too tired to	
		do the things I want to do	
Social Functioining	An16	I have to limit my social activity	-
		because I am tired	

FACIT-FATIGUE RESPONSE OPTIONS

All 13 items of the FACIT-Fatigue are measured on a Likert scale with 5 response options and range from 0 (Not at all) to 4 (Very Much).

FACIT-FATIGUE SCORING

To score the FACIT-Fatigue, reversals are first performed for the scores on two items (An5 and An7) then all individual items are summed to obtain a score. The sum of the item scores is multiplied by the number of items in the subscale, then divided by the number of items answered. This produces the final score which ranges from 0 to 52. Higher scores indicate less fatigue (Yellen et al.1997).

FACIT-FATIGUE RECALL PERIOD

The recall period of the FACIT-Fatigue is the past 7 days.

DATA

All data will stem from a single pivotal Phase III trial, REGENCY.

ANALYSES TO SUPPORT THE OBJECTIVE

RELIABILITY

Internal consistency - Internal consistency is an estimate of reliability based on the average correlation between items in a scale. This is represented by calculating Cronbach's alpha.

Calculate Cronbach's alpha using data from the 13 scale items in relation to the total FACIT-Fatigue scale score at Baseline. Cronbac's alpha ≥0.7 suggests reasonable internal consistency. In addition, estimates of lambda 2, 4, and omega will be calculated for comparison.

Test-retest reliability - Calculate two-way, mixed effects ICC between FACIT-Fatigue scores derived at Baseline and Week 24. Correlations ≥0.7 indicate reasonable test-retest reliability.

VALIDITY

Construct validity - assesses the degree to which a scale actually measures the construct it was designed to measure. Two estimates of construct validity will be used - convergent validity and discriminant validity.

Convergent validity - Tests if a scale is correlated with other scales that measure the same or related construct. Calculate Spearman's correlation coefficient and Weighted Kappa between:

- FACIT-Fatigue score and SF-36 Vitality, Physical Functioning, Bodily Pain, Role Physical, and General Health domain scores derived at Baseline
- FACIT-Fatigue score and SF-36 Physical Component Summary (PCS) score derived at Baseline

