In this section, the responsiveness of the FACIT-Fatigue score in relation to changes in disease status is assessed. For this analysis, the extent to which important longitudinal changes in Physician's Global Assessment (PGA), Subject's Global Assessment (SGA), and BILAG grade are associated with changes in the FACIT-Fatigue score will be examined. PGA and SGA score changes will be classified as better, worse, or unchanged, with a 30% increase or decrease used as the criterion for classifying meaningful change. BILAG grade change between consecutive assessments will be categorized as more active, stable, or less active. Moving from a BILAG score of D/E to C or vice versa will be classified as stable since those changes are not considered clinically meaningful. ANOVA will be used to compare mean FACIT-Fatigue score change between groups. Both analyses will be based on Week 76 data.

DERIVATION OF MINIMUM CLINICALLY IMPORTANT DIFFERENCE (MCID) - A RESPONDER THRESHOLD FOR ASSESSING WITHIN-PATIENT IMPROVEMENT

In order to derive an MCID for the FACIT-Fatigue scale, the SF-36 Vitality Domain as an anchor will be employed. The Vitality domain has the advantage of assessing a similar construct to the FACIT-Fatigue scale and is built from fairly well-delineated categorical response choices ("all of the time"=1; 'most of the time"=2; "a good bit of the time"=3; "some of the time"=4; "a little of the time"=5; and "none of the time"=6). For this analysis, an SF-36 Vitality domain responder will be defined as a patient who satisfies the following:

How much of the time during the past 7 days...

VT1 - did you feel full of pep? (must score a 3 or less);

VT2 - did you have a lot of energy? (must score 3 or less);

VT3 - did you feel worn out? (must score 4 or higher);

VT4 - did you feel tired? (must score 4 or higher)

The mean improvement in FACIT-Fatigue score (rounded up to the nearest integer) for the subpopulation of SF-36 VT responders between Baseline and Week 76 will serve as the estimated MCID for the FACIT-Fatigue scale. The proportion of subjects from each treatment group who have improved by the MCID value or greater between Baseline and Week 76 will be calculated. A chi-square test will be conducted to evaluate the differences

REFERENCES

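### The FACIT-Fatigue scoring rule in SAP Appendix 2 reverses the wrong items, so if programmed literally it gives 52 minus the intended score

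*SAP*

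**What the plan says.** SAP Appendix 2 sets a single coding for every item, in which the top value is the strongest endorsement: "All 13 items of the FACIT-Fatigue are measured on a Likert scale with 5 response options and range from 0 (Not at all) to 4". Its scoring paragraph then states that "reversals are first performed for the scores on two items (An5 and An7) then all individual items are summed to obtain a score". The sum is prorated (multiplied by 13, divided by the number of items answered), the range is given as 0 to 52, and the paragraph ends: "Higher scores indicate less fatigue".

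Three other places bear on the direction:

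- Protocol Section 4.5.7.2 gives the same 0 to 52 range, "with higher scores representing better patient status (less fatigue").
- SAP Section 4.3.1.6, the key secondary analysis of change to Week 76, says: "The FACIT-F scale for patients who died will be imputed with 0 (composite strategy").
- SAP Section 4.6.6, on eGFR and FACIT-F after Week 76, says: "Data after death will be imputed with 0".

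Protocol Appendix 10 reproduces the questionnaire with the same 0 to 4 response columns but has no scoring instructions. SAP Section 4.3.1.6 neither repeats the scoring rule nor refers to Appendix 2.

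**The concern.** The reversal clause and the stated direction cannot both be right. An5 (having energy) and An7 (being able to do usual activities) are the only items on which a high response means less fatigue. Reversing them aligns all 13 items so that a high value means more fatigue, and the total then runs the wrong way.

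FACIT-F is the sixth and last key secondary endpoint in the alpha-controlled sequence of SAP Section 2.1.1. If the sentence were programmed as it stands:

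- a benefit of obinutuzumab on fatigue would be estimated as harm;
- a death scored 0 would receive the best possible value instead of the worst;
- in Appendix 2, the SF-36 correlations and the direction of group differences would be reversed, and the step deriving the minimum clinically important difference (MCID) would fail.

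A range check would not detect the error, because the inverted score also runs from 0 to 52.

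**Working it through.** **Inputs from the documents.** Items are coded 0 to 4 and prorated by 13/n for n items answered (SAP Appendix 2). Eleven items are worded towards fatigue (HI7, HI12, An1 to An4, An8, An12, An14 to An16) and two away from it (An5, An7) (Protocol Appendix 10, SAP Appendix 2). Reversal means 4 minus the response.

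**Step 1: can the stated range and direction be reproduced?** The most fatigued patient answers 4 on the 11 items and 0 on An5 and An7. The least fatigued answers the opposite.

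| Items reversed | Most fatigued | Least fatigued |
|---|---|---|
| An5 and An7 (as written) | 11×4 + 2×4 = 52 | 0 |
| None | 11×4 + 2×0 = 44 | 2×4 = 8 |
| All 13 | 11×0 + 2×4 = 8 | 11×4 + 2×0 = 44 |
| The other 11 | 0 | 11×4 + 2×4 = 52 |

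As written, the range of 0 to 52 is reproduced but the direction is the opposite of the one stated. Only reversal of the other 11 items gives both.

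**Step 2: the relation holds for every patient.** If an answered item contributes y as written, it contributes 4 - y as intended. Over n answered items, the two prorated totals add to (13/n) × 4n = 52. So as-written = 52 - intended, with or without missing items. For example, with the 11 items at 1 and An5 and An7 at 3, the as-written score is 11×1 + 2×1 = 13, the intended score is 11×3 + 2×3 = 39, and 13 + 39 = 52.

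**Step 3: mean treatment difference.** Let p be the proportion of deaths in an arm, g the mean gain in survivors and B the intended baseline. The mean change in that arm is:

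- intended: (1 - p)g - pB
- as written: -(1 - p)g - p(52 - B)

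The two sum to -52p. The intended and as-written differences (obinutuzumab minus placebo) therefore sum to 52 × (placebo deaths - obinutuzumab deaths). They are mirror images only if the death proportions are equal.

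The documents give no expected FACIT-F effect, so gains of 5 vs 2 points and baselines of 25, 35 and 40 are assumed for illustration. The 2% vs 7% deaths are the Phase II figures in Protocol Section 1.3. The reaction count in Protocol Section 5.1.1.1 implies about 63 patients per arm (10/0.16 = 62.5), so this is roughly 1 vs 4 deaths.

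| Deaths | B | Intended | As written |
|---|---|---|---|
| None | any | +3.0 | -3.0 |
| 2% vs 2% | any | 0.98 × 3 = +2.94 | -2.94 |
| 2% vs 7% | 25 | +4.29 | -1.69 |
| 2% vs 7% | 35 | +4.79 | -2.19 |
| 2% vs 7% | 40 | +5.04 | -2.44 |

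For B = 35, intended: (0.98×5 - 0.02×35) - (0.93×2 - 0.07×35) = 4.20 - (-0.59) = +4.79. As written, with baseline 52 - 35 = 17: (-0.98×5 - 0.02×17) - (-0.93×2 - 0.07×17) = -5.24 - (-3.05) = -2.19. In all three unequal-death rows the two results sum to 52 × 0.05 = 2.60, so switching the sign of the as-written result afterwards would understate the intended difference by 2.6 points.

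With no deaths and complete data, reflecting both the response and the baseline changes only the sign of the ANCOVA estimate. The two-sided p-value is the same.

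**Step 4: MCID.** Appendix 2 takes as MCID "The mean improvement in FACIT-Fatigue score (rounded up to the nearest integer) for the subpopulation of SF-36 VT responders". Assume a true mean gain of 6.4. The intended MCID is 7. As written, the mean change is -6.4, which rounds up to -6. A signed cut-off of change ≥ -6 on the inverted score is an intended change of +6 or less. It would count patients with no change or more fatigue as improved, and exclude true gains above 6.

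**The case against.** The best counter-argument concerns reach. The sentence sits in a psychometric validation appendix, and Section 4.3.1.6 does not invoke it. The range, the direction and the death value agree everywhere else, and only one reversal pattern satisfies them, so a careful programmer could recover the right rule. The paragraph also cites a published scoring source that cannot be consulted here. FACIT-F is last in the sequence, so no later alpha-controlled test depends on it. A negative mean improvement among Vitality responders would probably expose the error at the MCID step.

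All of that limits the consequence, and most of it stands: the effect on the key secondary endpoint is conditional, and the documents do not show what has been programmed. The gains, baselines and MCID value above are assumptions, and the death percentages come from a handful of Phase II deaths. None of it makes the sentence correct. It is the only item-level rule in either document, SAP Section 5 says there is no additional supporting document, and following the rule gives the wrong answer. The fact that the error can be worked out is a reason to correct it.

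**Conclusion.** The reversal clause is wrong as written. From the documents' own item wording and coding, it yields exactly 52 minus the intended score for every patient; this needs no assumption. The stated direction and the death value of 0 are consistent with each other and with the protocol, so the reversal clause is the part to change.

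The effect on results depends on literal programming. In that case the FACIT-F treatment difference changes sign. If deaths differ between arms, the result is also distorted by 52 times the difference in death proportions (2.6 points at 2% vs 7%), which relabelling the direction would not repair. The primary endpoint, the other five key secondary endpoints, Cronbach's alpha, the test-retest ICC and the ANOVA F-tests are unaffected. It should be fixed, but it does not threaten the trial's main conclusion.

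**What to change.** In SAP Appendix 2, replace the reversal clause: reverse (4 minus response) the 11 items other than An5 and An7, and sum them with An5 and An7 as recorded. Leave the proration and the death value of 0 as they are, and state that 0 is the worst score and 52 the best. Refer to this rule from SAP Sections 4.3.1.6 and 4.6.6, so that the endpoint analyses and the validation work use the same derivation.

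Before death values are assigned, run the derivation program on two test records: no fatigue must return 52 and maximal fatigue 0. This check belongs in programming quality control and need not be written into the SAP.

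The cost is one clause, one clarifying statement, two cross-references and a two-record test. No data collection or patient procedure changes.

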3.1.2 Blinded Treatment

Randomized patients will receive blinded infusions of obinutuzumab 1000 mg or placebo on Day 1 and Weeks 2, 24, 26, 50, and 52 in three treatment groups according to

Figure 1 below. All patients will receive MMF (see Section 4.3.1.2) and corticosteroids (see Section 4.3.2.1). The primary endpoint, CRR, will be assessed at Week 76. Patients will be offered an optional renal biopsy following the Week 76 assessment (see Section 4.5.9).

Figure 1 Study Schema

All patients receive MMF and a prednisone taper

MMF=mycophenolate mofetil.

Eligibility for subsequent infusions after Week 76 will be determined based on the investigator's assessment of the adequacy of treatment response, need for intensification of therapy, and presence of unmanageable treatment-emergent adverse events according to the guidance provided in Table 1. The randomized treatment assignment will not be revealed during this process and investigators and patients will remain blinded until study unblinding occurs (see Section 3.1.5).

Table 1 Study Treatment after Week 76

Week 76 Response	Clinical Criteria, as Assessed by the Investigator	Subsequent Treatment
Adequate response	 Adequate response to treatment and No need for intensification of therapy and No unmanageable treatment-emergent adverse events 	Continue blinded infusions every 6 months
Inadequate response with some improvement from baseline	 Inadequate response to treatment and Clinically meaningful improvement from baseline in renal parameters or prior clinically meaningful improvement followed by worsening and Current need for intensification of therapy and No unmanageable treatment-emergent adverse events 	Open-label treatment (see Section 3.1.3)
All others	 Primary nonresponse: no clinically meaningful improvement at any time or Early discontinuation of blinded infusions or Receipt of rescue therapy a or treatment failure or Unmanageable treatment-emergent adverse events 	Study follow-up (see Section 3.1.4) and treatment with standard of care at the investigator's discretion

^a Except corticosteroid-only rescue (see Section 4.4.4.1).

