4.3.1.2 Mycophenolate Mofetil

All patients will receive MMF from the baseline visit (Day 1) onward. MMF will be titrated by Week 4 to a target dose of 2.0–2.5 g/day in divided doses. For patients newly initiating MMF, the recommended initial dosage is 1.5 g/day given in divided doses with titration by 500 mg/week to 2.0–2.5 g/day by Week 4.

If the investigator believes a patient requires MMF doses in excess of 2.5 g/day, the Medical Monitor should be contacted to discuss whether the target dose should be increased.

MMF should be maintained at the target dose through Week 80. Adjustments to MMF dosing will be permitted because of intolerance and adverse events. The dosage should not exceed 2.5 g/day unless discussed with the Medical Monitor. The guidelines for MMF dosing and recommended dose adjustments are provided in Appendix 7.

After Week 80, background immunosuppression may be adjusted at the discretion of the investigator. Investigators may continue MMF or switch to azathioprine (target dose: 2 mg/kg/day) as permitted by treatment guidelines. These therapies should be provided and monitored in a manner consistent with the ACR and/or EULAR/ERA-EDTA treatment guidelines (Hahn et al. 2012; Bertsias et al. 2012; Fanouriakis 2019), or local clinical practice.

MMF will be provided to the patient for home administration. To assess patient compliance with self-administration of MMF, patients will be required to record the date they took each dose in a medication diary; missed doses will also be recorded. Patients will be instructed to bring all unused study medication and their medication diaries at specified study visits for assessments of compliance.

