4.3.2 Additional Medications

4.3.2.1 Corticosteroid Administration

All patients will receive IV and oral corticosteroids for the treatment of LN, consistent with ACR and EULAR/ERA-EDTA treatment guidelines (Hahn et al. 2012; Bertsias et al. 2012; Fanouriakis 2019). Every effort must be made to follow the corticosteroid regimen described below to permit the primary comparison of obinutuzumab and placebo.

Intravenous Corticosteroid Treatment

During the 6 months prior to screening, during screening, or on Day 1 (prior to the first infusion), all patients must have received at least one dose of pulse-dose methylprednisolone IV (250–1000 mg) or equivalent for the treatment of the current episode of active LN. Where possible, pulse corticosteroids should be completed prior to screening. The maximum permitted dose of pulse corticosteroids during the 4 weeks prior to screening or during screening is 3 g methylprednisolone IV or equivalent. If not given during the 6 months prior to screening or during screening, a single dose of pulse-dose methylprednisolone IV (250–1000 mg) will be given in place of pre-infusion methylprednisolone 80 mg IV on Day 1 only (see Section 4.3.2.2).

At blinded obinutuzumab or placebo infusions at Day 1 and Weeks 2, 24, 26, 50, and 52, methylprednisolone 80 mg IV will be given to prevent IRRs (see Section 4.3.2.2). Oral prednisone should not be administered on days when pre-infusion methylprednisolone is given.

Oral Prednisone Treatment

All patients will receive oral prednisone and follow a standardized tapering schedule through Week 80. In regions where prednisone or the specified dose of prednisone is not readily available, an approximately equivalent dose of an oral corticosteroid with a similar duration of action may be substituted (see Appendix 4).

During screening, prednisone may be administered up to 0.5 mg/kg/day (maximum 60 mg/day) if clinically indicated. Oral prednisone should not be administered on all days when pre-infusion methylprednisolone is given.

On Day 2, all patients will receive oral prednisone 0.5 mg/kg/day (maximum 60 mg/day) and remain at this dose until the Week 2 visit. Beginning on Day 15, prednisone will be tapered to achieve a target dose of 5 mg/day by Week 24 according to the schedule in Table 2. Prednisone will be maintained at 5 mg/day from Week 24 until Week 80.

Table 2 Prednisone Tapering Schedule through Week 80

	Prednisone Dose (mg/day) ^a			
Days 2-14	30	40	50	60
Week 2	25	30	40	50

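### The FACIT-Fatigue test-retest ICC runs from Baseline to Week 24 in all patients, so real change in fatigue can pull a reliable scale below the 0.7 criterion

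*SAP*

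**What the plan says.** SAP Appendix 2 sets out the psychometric validation of FACIT-Fatigue, intended to support its inclusion in the US label. For test-retest reliability it says: "Calculate two-way, mixed effects ICC between FACIT-Fatigue scores derived at Baseline and Week 24". The yardstick is: "Correlations ≥0.7 indicate reasonable test-retest reliability". It does not say whether the ICC measures absolute agreement or consistency, and it does not limit the analysis to patients whose condition is unchanged. It also notes: "The recall period of the FACIT-Fatigue is the past 7 days".

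The protocol describes what happens between those two visits:
- Section 3.1.2: "Randomized patients will receive blinded infusions of obinutuzumab 1000 mg or placebo on Day 1 and Weeks 2, 24, 26, 50, and 52". The Day 1 and Week 2 infusions fall inside the interval.
- Section 4.3.1.2: "MMF will be titrated by Week 4 to a target dose of 2.0–2.5 g/day in divided doses".
- Section 4.3.2.1: "Beginning on Day 15, prednisone will be tapered to achieve a target dose of 5 mg/day by Week 24". The planned dose then stays at 5 mg/day until Week 80.

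Patients enter with active or active/chronic Class III or IV disease and a UPCR of at least 1 g/g (Protocol 4.1.1). FACIT-F, PGA and SGA are scheduled at Baseline and Weeks 24, 50 and 76 (Protocol Appendix 1, Table 1), so there is no short-interval retest.

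The responsiveness part of Appendix 2 already contains a stability class: "PGA and SGA score changes will be classified as better, worse, or unchanged", with a 30% change as the cut-off. The reliability analysis does not use it.

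**The concern.** Test-retest reliability asks whether the instrument returns the same score when the patient's state has not changed. Baseline to Week 24 is the interval in which this trial sets out to change that state. A patient whose fatigue truly improves or worsens then contributes to the ICC as if the questionnaire had been inconsistent.

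The appendix also works against itself. Its responsiveness section looks for FACIT-Fatigue to move with disease status, and change in the score is a key secondary endpoint. The better the scale does on responsiveness, the worse it may look on test-retest.

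What is at stake is the sponsor's own validation case. A value below 0.7 would leave open whether the scale is unreliable or the patients changed.

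**Working it through.** The plan states no expected ICC and no sample size for this analysis; 0.7 is a criterion, not a derived figure. There is nothing to reproduce, so the check asks how far real change can move the ICC.

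**Assumed inputs (none are in the documents).** True-score SD at Baseline 10 points, so variance 100. Scale reliability R = 0.85 or 0.90. True change to Week 24 has mean d and SD s and is independent of the Baseline true score.

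**Formulas, two visits.**
- Error variance: e = 100 × (1 − R)/R, which is 17.65 for R = 0.85 and 11.11 for R = 0.90.
- Visit variances: v1 = 100 + e; v2 = 100 + s² + e. Covariance = 100.
- Consistency ICC = 100 / [(v1 + v2)/2] = 100 / (100 + e + s²/2).
- Absolute-agreement ICC = 100 / (100 + e + s²/2 + d²/2).

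| R | s | d | Consistency | Absolute agreement |
|---|---|---|---|---|
| 0.85 | 6 | 2 | 100/135.65 = 0.74 | 100/137.65 = 0.73 |
| 0.85 | 8 | 4 | 100/149.65 = 0.67 | 100/157.65 = 0.63 |
| 0.85 | 10 | 5 | 100/167.65 = 0.60 | 100/180.15 = 0.56 |
| 0.90 | 8 | 4 | 100/143.11 = 0.70 | 100/151.11 = 0.66 |

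**Where the criterion is crossed (consistency).** Setting 100/(100 + e + s²/2) = 0.7 gives s² = 2 × (142.86 − 100 − e). For R = 0.85, s² = 50.4 and s is about 7.1 points. For R = 0.90, s² = 63.5 and s is about 8.0 points.

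**Second parameterisation, as a check.** Suppose instead that the variance is equal at both visits and true fatigue correlates ρ between them. The consistency ICC is then R × ρ. It falls below 0.7 when ρ < 0.7/R, which is 0.824 for R = 0.85 and 0.778 for R = 0.90.

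Simulation with 252 patients (the planned enrolment) and 2,000 runs per case, R = 0.90, no mean shift:
- ρ = 1: mean ICC 0.90, no run below 0.7.
- ρ = 0.90: mean 0.81, no run below 0.7.
- ρ = 0.70: mean 0.63, 98% of runs below 0.7.

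**Mean shift alone.** With R = 0.90, ρ = 1 and a shift of 0.5 SD common to all patients, consistency stays at 0.90. Agreement falls to 0.90/(1 + 0.5²/2) = 0.80.

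**Stable patients.** With s = 0 and d = 0 both forms return R, so the ICC estimates what it is meant to estimate.

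**The case against.** Several counter-arguments have force.

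- **Direction and size are not certain.** Under consistency a shift common to all patients does no harm; the loss needs change that varies between patients. Two treatments, and responders pooled with non-responders, make that plausible, but the documents do not quantify it. At a true-change SD of 6 a scale with reliability 0.85 still passes under either form.
- **Fatigue may not follow nephritis activity closely.** Appendix 2 cites evidence that fatigue is about as frequent with active LN as without it. Some patients also take mycophenolate before entry (Protocol 4.3). Titration and the steroid taper still fall within the interval.
- **The consequence is limited.** No decision rule hangs on 0.7. The appendix also plans Cronbach's alpha, lambda 2, lambda 4 and omega, and the protocol already describes the scale as validated in SLE. Because real change will usually lower the ICC, a pass would still be reassuring.
- **Week 50 to Week 76 is not clean.** It is about 26 weeks against a 7-day recall, with infusions at Weeks 50 and 52. The constant prednisone dose is only the plan: increases for flares are permitted, and the SAP allows that some patients stop oral steroids. A 30% relative rule on a 100-mm scale is also unstable at low scores.

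These points limit the claim and shape the remedy. None supplies the missing stability condition.

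A reader might infer that the ICC will be biased down, or that the scale will wrongly be shown unreliable. The documents support neither: they give no FACIT-F SD, reliability or change data, and the ICC is only one of several reliability measures.

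**Conclusion.** The point holds as a flaw of method. The planned ICC mixes measurement error with real change, so a reliable scale can fall below 0.7 and a failing result would have no clear meaning.

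Under the assumed inputs, reliability 0.85 becomes 0.56 to 0.73 for absolute agreement and 0.60 to 0.74 for consistency. The agreement figures include the mean shifts of 2 to 5 points, so the change SD alone does not account for all of the fall. With reliability 0.90, change SD 8 and shift 4, consistency is 0.699, essentially at the criterion. The mechanism is firm; the size depends wholly on these assumptions.

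It would also be wrong to read this as a threat to the efficacy results. Type I error, power and the FACIT-F comparison, which is last in the SAP's testing sequence, do not depend on this ICC. The issue is confined to the psychometric support for the label.

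**What to change.** In the reliability part of SAP Appendix 2:

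1. Make the main test-retest ICC the one in patients classed as unchanged on both PGA and SGA by the appendix's existing 30% rule. This restriction is the essential part.
2. Preferably compute it between Week 50 and Week 76, when the planned prednisone dose is constant.
3. State the ICC form: absolute agreement, with consistency alongside.
4. Report how many patients are included.
5. Keep the Baseline to Week 24 ICC as descriptive only, not judged against 0.7.
6. Acknowledge as limitations the gap of about 26 weeks and the infusions at Weeks 50 and 52.

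The cost is appendix wording; the assessments are already scheduled. The price is a smaller, selected sample, whose size cannot be estimated from the documents.
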